**(1) NCS criteria:**

For the NCS, the motor responses of median and ulnar nerves in the bilateral upper limb and the fibular and tibial nerves in the bilateral lower limb and the sensory responses of median and ulnar nerves in the bilateral upper limb and sural and medial plantar nerves in the bilateral lower limb were recorded. Nerve conduction parameters recorded included distal motor latency (DML), peak to peak sensory nerve action potential amplitude, motor nerve conduction velocity (MNCV), and sensory nerve conduction velocity (SNCV). Pediatric individuals who are at least 4 years old are deemed to have achieved the NCS reference ranges typically seen in adults.[14] The reference values for each nerve were according to reference limits of NCS parameters for Chinese subjects from Fong et al. as follows:

Table 1 Reference lists of NCS parameters for Chinese subjects and range in all subjects

Parameters	Reference limits	Range all subjects	
	Chinese		
Motor			
Median			
DML (ms)	4.1	2.5-4.3	
Amplitude (mV)	7.3	7.0-17.9	
MNCV (m/s)	52	50-65	
Ulnar			
DML (ms)	3.0	2.0-3.1	
Amplitude (mV)	6.4	6.3-15.6	
MNCV (m/s)	53	52-68	
Fibular			
DML (ms)	4.2	2.6-4.4	
Amplitude (mV)	3.3	2.4-10.9	
MNCV (m/s)	43	42-58	
Tibial			
DML (ms)	3.9	2.4-4.3	

Amplitude (mV)	7.5	5.1-26.7
MNCV (m/s)	41	38-57
Sensory		
Median		
Amplitude (mV)	7	5-34
SNCV (m/s)	48	45-67
Ulnar		
Amplitude (mV)	6	2-22
SNCV (m/s)	48	46-66
Sural		
Amplitude (mV)	6	2-34
SNCV (m/s)	42	38-61
Medial plantar		
Amplitude (mV)	3	2-37
SNCV (m/s)	40	26-36

NCS parameters including distal latencies, amplitudes, and velocities were considered abnormal, if values were more than 2.0 standard deviation of the normal reference values. In our study, the pediatric neurologist considered CIPN as the presence of abnormal NCS parameters in two or more nerves.

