### ***Clinician diagnosis of pediatric CIPN***

In our previous systematic review of assessment measures for CIPN among pediatric oncology patients(reference), it was concluded that the method of choice for assessing pediatric CIPN was combination of subjective and objective assessment measures. The diagnosis of pediatric CIPN in our study was established solely if the abnormal Nerve Conduction Studies (NCS) criteria, NCI-CTCAE score  $\geq 2$ , and clinical consultation (including the chemotherapeutic drugs used, cumulative doses, and clinical characteristics and time course of neuropathy symptoms) of CIPN symptoms were simultaneously observed based on the consensus of pediatric neurologists in the three hospitals.

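### Table 1 labels the four sensory amplitude limits in millivolts, the motor unit; this is probably a unit error in a table that feeds the reference diagnosis of CIPN

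*Protocol*

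**What the plan says.** Under Clinician diagnosis of pediatric CIPN, the reference diagnosis is "established solely if the abnormal Nerve Conduction Studies (NCS) criteria", a CTCAE score of at least 2 and a clinical consultation are all met together, by consensus of the neurologists at the three hospitals.

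The NCS criteria list "peak to peak sensory nerve action potential amplitude" among the recorded parameters and take the thresholds from Table 1. The four sensory amplitude rows are median "Amplitude (mV) 7 5-34", ulnar "Amplitude (mV) 6 2-22", sural "Amplitude (mV) 6 2-34" and medial plantar "Amplitude (mV) 3 2-37". The motor rows carry the same unit; the median motor row is "Amplitude (mV) 7.3 7.0-17.9". No other part of the protocol gives a unit for sensory amplitude.

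A parameter counts as abnormal when it lies more than 2.0 SD from the normal reference values; no SD is printed. The neurologist then "considered CIPN as the presence of abnormal NCS parameters in two or more nerves".

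**The concern.** The table makes the sensory response of a nerve reach higher than the motor response of the same nerve. Sensory potentials recorded at the skin are generally understood to be far smaller than motor responses, so a shared millivolt label suggests that the unit was carried down from the motor block.

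Table 1 supplies the thresholds for one of three conditions that must all hold for the reference diagnosis. Under Validity assessment, that diagnosis is the criterion for the Spearman correlation, the ROC curve, the AUC and the Youden cut-off of the P-CIN. A wrong unit here could change who counts as a case, and so the accuracy figures the study reports.

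**Working it through.** The plan states no calculated figure to reproduce, so the check is one of units.

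**Inputs from Table 1.** Sensory limits and ranges: median 7 (5-34), ulnar 6 (2-22), sural 6 (2-34), medial plantar 3 (2-37). Motor ranges of the two nerves tested both ways: median 7.0-17.9, ulnar 6.3-15.6. All are labelled mV.

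**Assumption, not in the documents.** Sensory potentials are of microvolt order, and the printed sensory numbers are microvolt values.

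**Step 1: same nerve, as printed.** Ratio of the top of the sensory range to the top of the motor range:
- median: 34 / 17.9 = 1.90
- ulnar: 22 / 15.6 = 1.41

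**Step 2: literal reading, with the printed limit as the cut-off.** Value in mV = value in microvolts / 1000. The shortfall is the limit divided by the top of the range.

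| Sensory nerve | Top of range, mV | Printed limit, mV | Limit / top of range |
|---|---|---|---|
| Median | 34/1000 = 0.034 | 7 | 206 |
| Ulnar | 22/1000 = 0.022 | 6 | 273 |
| Sural | 34/1000 = 0.034 | 6 | 176 |
| Medial plantar | 37/1000 = 0.037 | 3 | 81 |

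Even the largest value in each range falls below its limit. All four sensory nerves would be abnormal (4 x 2 sides = 8 of the 16 bilateral motor and sensory recordings), and two are enough to meet the NCS rule.

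**Step 3: the written 2.0 SD rule, applied to the printed limit.** Cut-off = limit - 2 x SD, which is negative once SD > limit / 2:
- median: 7/2 = 3.5
- ulnar and sural: 6/2 = 3
- medial plantar: 3/2 = 1.5

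With SDs above these values no child would be abnormal on sensory amplitude, and the motor and velocity parameters would decide the NCS result. With clearly smaller SDs the result of step 2 returns. The protocol gives no SD, so it does not settle which applies.

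**Step 4: the same numbers read in microvolts.** The limits 7, 6, 6 and 3 each lie inside their own printed range (5-34, 2-22, 2-34, 2-37). The rows can then separate children, and no number needs to change.

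**The case against.** The strongest objection is that the point hangs on one character in a machine-read table that breaks across a page; a micro sign may have been lost. That cannot be excluded. Against it, chi-square and greater-or-equal signs survived elsewhere in the text, and all four sensory rows agree. The protocol page has to be looked at before anything is changed.

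Second, limits and ranges share one unit, so each sensory amplitude row is consistent within itself. This is true. What the document alone shows is the oddity between the sensory and motor rows; the microvolt scale comes from outside it.

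Third, neurophysiology laboratories that report sensory amplitude in microvolts would apply 7, 6, 6 and 3 correctly, and a literal reading that flagged every child would soon be noticed. This stands, and it limits the likely harm in practice.

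A reader might infer that every child fails the sensory limits, that NCS specificity is 0%, or that the hospitals will differ because some convert the unit and others do not. The documents do not support these as flat statements. The first two need both the microvolt assumption and the printed limit as cut-off, whereas the written rule is 2.0 SD with no SD given. Nothing in the protocol indicates that sites will handle the unit differently.

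**Conclusion.** The point holds as a probable unit error in a decision table, with moderate confidence. The label makes sensory responses reach 1.4 to 1.9 times the motor maximum of the same nerve. If sensory potentials are of microvolt order, the printed limits are about 80 to 270 times the top of the corresponding ranges.

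Only if the printed limits are also used as the cut-offs would the NCS condition be met by every child. Even then the diagnosis would not be emptied, because the CTCAE and consultation conditions still have to be met. Under the 2.0 SD rule the consequence is undetermined. The point deserves correction because the table sets thresholds for the criterion behind the AUC and cut-off, not because a failed criterion has been shown.

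**What to change.** 1. Look at the protocol page itself to confirm that the four sensory amplitude rows print mV, and check the unit in the cited Chinese reference table.
2. If the protocol prints mV and the source gives microvolts, change the unit of the median, ulnar, sural and medial plantar sensory amplitude rows and leave the numbers as they are.
3. Fix that unit on the data-entry form at all three hospitals before any NCS result is classified.

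If the page already shows microvolts, Table 1 needs no change on this point.

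The cost is four labels and one data-entry field, with no added patients or procedures. The absent SDs are a separate matter, as is the medial plantar velocity row, whose limit of 40 m/s lies outside its own range of 26-36 m/s; that row can be checked while the source table is open.

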### ***Validity assessment***

Validity refers to an instrument measures exactly what it proposes to measure. Validity can be assessed in different forms such as content validity, convergent validity, criterion validity, and construct validity. **Content validity** can be defined as the extent to which an assessment tool accurately and fully reflects the concept being measured. The Delphi technique will be used to establish the content validity of the P-CIN. We will obtain the opinions of 10 experts through a structured questionnaires delivered two iterations until consensus will be reached. **Convergent validity** is the degree to which scores on a measure associate with scores on other measures that are intended assess similar constructs. Pain level, self-reported quality of life are CIPN-related concepts that have been identify pediatric oncology patients with CIPN risk[15]. Therefore, convergent validity will be explored using well-established CIPN-related measurements, namely, (1) the Wong-baker FACES pain rating scale to assess levels of pain; and (2) the Pediatric Quality of Life Inventory (PedsQL) Cancer Module to determine level of quality of life with the help of the Spearman's correlation coefficient (r). **Criterion validity** is the relation between the score of a certain instrument and some external criterion. This criterion has to be a widely accepted measure, with the same characteristics of the assessment tool. Criterion validity will be evaluated using the pediatric neurologists' CIPN diagnosis as a reference criterion. Spearman's correlation coefficient (r) will be calculated to evaluate the correlations between the P-CIN and the CIPN diagnosis. Using diagnostic testing to determine the presence or absence of the CIPN is essential. The ROC curve aims to find an optimal cut-off value with the best CIPN diagnostic performance. Additionally, the ROC curve is utilized to evaluate the overall diagnostic performance of a test and to compare multiple diagnostic tests.[23] The area under the curve (AUC) will be used to measure the accuracy of diagnostic test. Generally, an  $AUC \geq 0.8$  is considered acceptable. Youden statistic (calculated as sensitivity + specificity - 1) was used to determine the optimal cut-off value.[24] The point at which this value is maximized is determined as the optimal cut-off value.[24]

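### The 2.0-SD rule for abnormal nerve conduction does not fit Table 1, which gives limits and ranges but no means or SDs; one row of the table also needs checking

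*Protocol*

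**What the plan says.** Under Clinician diagnosis of pediatric CIPN, the protocol makes nerve conduction one of three requirements that must be met together: "The diagnosis of pediatric CIPN in our study was established solely if the abnormal Nerve Conduction Studies (NCS) criteria", a CTCAE score of at least 2 and the clinical consultation "were simultaneously observed based on the consensus of pediatric neurologists in the three hospitals".

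Under (1) NCS criteria, the source of the normal values is given as follows: "The reference values for each nerve were according to reference limits of NCS parameters for Chinese subjects". Table 1, captioned "Reference lists of NCS parameters for Chinese subjects and range in all subjects", has 20 parameter rows and two data columns: a limit for Chinese subjects and a range for all subjects. After the table comes the abnormality rule: "NCS parameters including distal latencies, amplitudes, and velocities were considered abnormal, if values were more than 2.0 standard deviation of the normal reference values". CIPN on nerve conduction is then "the presence of abnormal NCS parameters in two or more nerves".

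Under Validity assessment, the neurologists' diagnosis is used for criterion validity: "CIPN diagnosis as a reference criterion". It also serves the ROC analysis: "The ROC curve aims to find an optimal cut-off value with the best CIPN diagnostic performance".

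**The concern.** A 2-SD rule needs a centre and an SD. The protocol prints neither for any NCS parameter, and the figures it calls reference values are limits. The rule as written therefore cannot be run from the table as written. The one literal way of combining them, going 2 SD beyond the tabulated limit, counts the margin of normality twice. The text also does not say on which side of each limit a value is abnormal.

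Because the NCS criterion is required, a rule that is harder to meet can only leave the number of CIPN-positive children unchanged or reduce it. Three results depend on that classification: the Spearman correlation of P-CIN with the diagnosis, the AUC and the Youden cut-off. Internal consistency, test-retest reliability, factor analysis, convergent validity and feasibility do not use it. If the three hospitals read the sentence differently, identical recordings could be classified differently.

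A smaller matter is that one row of Table 1, medial plantar SNCV, contradicts itself as printed.

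**Working it through.** **1. Three readings of the rule**

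- A: the tabulated limits are the cut-offs. This can be run from Table 1, but the text does not say it.
- B: the cut-off is mean ± 2 SD. This cannot be run from the protocol, since neither figure is given. If the limits were themselves derived this way, B and A coincide, but that is not stated.
- C: the cut-off is the tabulated limit ± 2 SD. This is the literal reading, and it also needs an SD.

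**2. Reading C for the sensory amplitudes**

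Limits and ranges are from Table 1. The SD is my assumption: range width/4 to range width/6. Low amplitude is taken as the abnormal side, so the cut-off is limit - 2 × SD.

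| Nerve | Limit | Range | Width | Cut-off, SD = width/4 | Cut-off, SD = width/6 |
|---|---|---|---|---|---|
| Median | 7 | 5-34 | 29 | 7 - 14.5 = -7.5 | 7 - 9.7 = -2.7 |
| Ulnar | 6 | 2-22 | 20 | 6 - 10.0 = -4.0 | 6 - 6.7 = -0.7 |
| Sural | 6 | 2-34 | 32 | 6 - 16.0 = -10.0 | 6 - 10.7 = -4.7 |
| Medial plantar | 3 | 2-37 | 35 | 3 - 17.5 = -14.5 | 3 - 11.7 = -8.7 |

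All eight cut-offs are negative, and a peak-to-peak amplitude cannot be. The cut-off is negative whenever the SD exceeds half the limit, that is 3.5, 3.0, 3.0 and 1.5. In terms of the assumption, the cut-off stays negative while the SD is larger than width/8.3 (58/7), width/6.7 (40/6), width/10.7 (64/6) and width/23.3 (70/3). The ulnar row is the closest call.

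**3. Readings A and C on a velocity**

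Median MNCV has limit 52 m/s and range 50-65, so the width is 15. Under A the cut-off is 52. Under C it is 52 - 7.5 = 44.5 (SD = 15/4) to 52 - 5.0 = 47.0 (SD = 15/6). The two readings differ by 5.0 to 7.5 m/s.

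**4. Internal check of Table 1**

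For each row I checked minimum ≤ limit ≤ maximum and computed (limit - minimum)/(maximum - minimum).

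- In 19 of 20 rows the limit is inside its range. The four distal latencies sit 79-91% of the way up, and the 15 amplitudes and other velocities 1-20% of the way up.
- Medial plantar SNCV gives (40 - 26)/(36 - 26) = 140%, that is 4 m/s above the maximum.

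The other seven velocity rows compare as follows:

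| | Other seven velocity rows | Medial plantar SNCV |
|---|---|---|
| Limit (m/s) | 41 to 53 | 40 |
| Range minimum (m/s) | 38 to 52 | 26 |
| Range width (m/s) | 15 to 23 | 10 |
| Limit minus minimum (m/s) | 1 to 4 | 14 |

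The printed limit is close to the others, whereas the printed range lies wholly below every other velocity minimum and is narrower than any other. That points to the range as the faulty figure. It is an indication only, since motor and sensory nerves of different limbs are being compared.

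**The case against.** The best defence is that a reference limit ordinarily is the boundary of normal, so the 2.0-SD sentence may merely describe how the boundary was set. Reading C gives unusable amplitude cut-offs, so a neurologist would not apply it. The position of the limits also shows the direction in 19 of 20 rows. The cited source may print means and SDs, and the consensus of neurologists may have settled the matter. Most of this stands: reading A is the likely intent, and the claim that the rule cannot be run is true of the wording, not necessarily of practice. But the protocol presents its reference values in Table 1 and then adds the margin in a separate sentence. It records neither reading A nor any other.

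A reader might infer from the medial plantar row that every child within the printed range would be called abnormal, and that one of the two required nerves is thereby supplied. The document does not support that. It would need the limit to be the wrong figure and to be used as a lower cut-off. The likelier fault is in the range, which no decision rule uses, and a digit misread in the PDF cannot be excluded. Even if the limit were wrong, the number of nerves supplied is undetermined: the nerve is recorded on both sides, and the text does not say whether left and right count separately. The CTCAE and clinical requirements would still have to be met, so this row alone cannot create a diagnosis.

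**Conclusion.** The abnormality rule and Table 1 do not fit together as printed. This is more than a detail left for later, because the protocol states both and they conflict. Under reading C, with the SD assumed between width/4 and width/6, none of the four sensory amplitudes could ever be abnormal. The statement that the table lacks means and SDs needs no assumption.

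It would be tempting to conclude that the AUC or the Youden cut-off is biased. The protocol does not allow that: it gives no NCS distribution or CIPN prevalence, and the reading in use is unknown. Confidence is high that the wording is inconsistent and low that any result changes.

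The medial plantar SNCV row is secondary. It is the only inconsistent row of 20 and should be checked; if the range is the faulty figure, no cut-off is affected. Overall severity is minor.

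**What to change.** 1. Reconcile the 2.0-SD sentence with Table 1 and the cited source. Either state that the tabulated limits are the cut-offs and in which direction each applies, or print the means and SDs that the rule needs.
2. Check the medial plantar SNCV row against the original document and the source, and correct whichever figure is wrong. No particular value is proposed here.
3. State whether left and right recordings of one nerve count as one nerve or two.
4. Apply the one reconciled rule to all recorded NCS at the three hospitals before the AUC or the cut-off is estimated.

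The cost is one table check, a sentence or two of text, and a re-reading of recorded values. No new patients or procedures are needed.

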## **(2) National Cancer Institute Common Terminology Criteria for Adverse Events (NCI-CTCAE) Version 5.0**

The CTCAE (version 5.0) consists of over 330 items scoring adverse events (AE) due to cancer treatment divided into 26 different categories. Grade refers to the severity of the adverse events. Possible grades range from grade 1 (Mild, asymptomatic or mild symptoms, clinical or diagnostic observations only), grade 2 (Moderate; minimal, local or noninvasive intervention indicated; limiting age-appropriate instrumental Activities of Daily Living (ADL)), grade 3 (Severe or medically significant but not immediately life-threatening; hospitalization or prolongation of hospitalization indicated; disabling; limiting self-care ADL), grade 4 (Life-threatening consequences; urgent intervention indicated) to grade 5 (Death related to AE). The NCI-CTCAE items used for the assessment of CIPN are peripheral sensory neuropathy, peripheral motor neuropathy, constipation, diarrhea, and neuralgia due to the sensory, motor and autonomic symptoms of pediatric CIPN[15]. The maximum CTCAE sum score of these 5 items is 22. Participants with a total score of 2 or higher are considered to have CIPN[16, 17].

***Wong-baker FACES Pain Rating scale***

This scale combines pictures and numbers to enable the user to rate pain which demonstrates six faces with increasing degree of pain from left to right, where each face is rated on a scale of 10 in which 0 indicated no hurt, 2 indicated hurts a little, 4 indicated hurts little more, 6 indicated hurts, even more, 8 indicated hurts a whole lot, 10 indicated hurts worst[18]. It can be used for children over the age of 3, and for adults[18]. This scale has adequate psychometric properties and it is easy and quick to[19] and it has been validated among Chinese children with acute fever[20].

### ***Chinese version of the Pediatric Quality of Life Inventory (PedsQL) Cancer Module***

The PedsQL Cancer Module will be used to assess the participants' QoL. This scale contains 27 items grouping into eight subscales including (1) pain and hurt, (2) nausea, (3) procedural anxiety, (4) treatment anxiety, (5) worry, (6) cognitive problems, (7) perceived physical appearance, and (8) communication. There are parallel and identical versions for pediatric patients (young child: 5-7 years old, child: 8-12 years old, and adolescent: 13-18 years old) and parents (toddler: 2-4 years old plus the above three age groups). The participants rated how frequently a particular problem occurred in the past month, using a three-point Likert scale (0 = Never, 2 = Sometimes, 4 = Almost always) for children 5-7 years old and a five-point Likert scale (0 = Never, 1=Almost never, 2=sometimes, 3=often, 4 = Almost always) for children of 8-18 years old and for the parents of patients of all ages. Each item score will be reversely scored and then linearly transformed into 0-100 scale (0 = 100, 1 = 75, 2 = 50, 3 = 25, 4 = 0). The scale is the average of the total item scores. Higher scores represent better quality of life (QoL). The psychometric properties of the Chinese version of the scale have been well-examined[21]. This scale has been demonstrated as a valid and reliable tool in assessing QoL for Hong Kong Chinese adolescent with cancer[21].

### ***Psychometric evaluation***

#### ***Reliability assessment***

Reliability refers to the ability of a instrument to determine that a measurement yields reproducible and consistent results. Three important reliability criteria are: internal consistency, and stability. **Internal consistency** shows if all subparts of an instrument measure the same characteristic. Cronbach's alpha coefficient and the corrected item-total correlation will be used to assess internal consistency of the P-CIN. **Stability** estimates the consistency of measurement repetition and can be performed using test-retest method. The time span between measurements will influence the interpretation of test-retest reliability; therefore, the time span from 10 to 14 days is considered adequate for the test and retest. A group of 50 children will be randomly selected for the achievement of statistical significance for an alpha value is 0.05 and with a power of 0.90.[22] The intraclass correlation coefficient (ICC) is one of the most used tests to estimate continuous variables stability, as it takes into

account the measurement errors.

